## II. OBJECTIVES

### A. PRIMARY OBJECTIVES

1. To describe identification of potential TRALI cases, risk factors for TRALI, and relevant transfusion exposures in HCA's Sentinel database
2. To describe incidence rates of TRALI subsequent to plasma, platelet, packed red blood cell administration using HCA's Sentinel database
3. To determine through medical chart review the performance of an ICD-9-CM code based algorithm for identifying TRALI
4. To determine through medical chart review the positive predictive value of reported transfused product exposure in identified TRALI cases

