## 2. Calculation of Incidence Rates

Unadjusted incidence rates of TRALI occurrence after any transfusion will be calculated, along with 95% confidence intervals. Any transfusion will be defined as exposure to plasma, platelets (PLT), or packed red blood cells (RBC) as defined in HCA's Sentinel database. TRALI will be defined using ICD-9-CM based codes in HCA's Sentinel database, and the primary analysis will focus on TRALI as defined by criterion A (Table 5). Unadjusted TRALI rates (per 100,000 inpatient transfusion stays) will be stratified by year, blood component groups (i.e., plasma, PLT, and RBC), age, sex, race, and quantified units. If data on the number and type of component unit(s) transfused are available, unadjusted TRALI rates per number of units transfused will also be calculated. If feasible, quantified units will be examined separately for children and adults.

In addition to identifying rates of TRALI occurrence after any exposure to plasma, PLT, or RBC during an inpatient stay, if adequate sample size is available we will also explore exposure to RBC-only, plasma-only, and PLT-only. Exposure to multiple blood component types (i.e., plasma and PLT, RBC and PLT, plasma and RBC, plasma and RBC and PLT) or non-specific blood components (if relevant) will also be described.

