#### **4. Exploratory Analyses**

The potential for comparing blood component specific TRALI incidence rates will be explored, and if feasible a reference category will be defined for variables examined in the primary analysis and unadjusted rate ratios and 95% confidence intervals will be calculated.

The workgroup will also explore the ability to identify specific categories of blood components within HCA data, including component type and processing method (e.g., leukocyte-reduced, irradiated), and will provide descriptive analyses. If feasible and available, exposure information retrieved from charts, such as method of blood component processing and timing of administration, will be compared to information in HCA's Sentinel transfusion table. Similarly, the feasibility of examining distribution of possible patient level and transfusion level TRALI risk factors not explored in primary analyses and relevant comorbidities will be examined as part of these exploratory analyses.

Descriptive statistical analyses comparing transfusion stays with TRALI vs without TRALI by demographic characteristics (age, gender, race), length of stay, mechanical ventilation (identified with ICD-9-CM procedure codes) and by inpatient mortality will also be conducted.

The workgroup will explore methods to reduce missing transfusion information in HCA's Sentinel database. If feasible, this exploration will utilize internal investigations with HCA staff to determine what may be possible, and/or development of alternate code lists to identify specific transfusion exposures. Finally, the workgroup will identify HCA data elements that are included in the SCDM that are useful/relevant for studying TRALI and data elements relevant to TRALI that are not included in the SCDM.

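### The plasma, platelet and RBC strata overlap, the exploratory component rate ratios are not confined to exclusive groups, and the electronic rates have no rule that keeps post-onset transfusions out

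*Protocol*

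**What the plan says.** Section II.A makes it a primary objective "To describe incidence rates of TRALI subsequent to plasma, platelet, packed red blood cell administration". Section IV.F.2 expresses the rates per 100,000 inpatient transfusion stays, and they "will be stratified by year, blood component groups (i.e., plasma, PLT, and RBC), age, sex, race, and quantified units". The next paragraph describes them as "rates of TRALI occurrence after any exposure to plasma, PLT, or RBC during an inpatient stay". Exclusive groups are an addition: "if adequate sample size is available we will also explore exposure to RBC-only, plasma-only, and PLT-only". The four multi-component combinations are to be described, but the section does not say that such stays leave the plasma, PLT and RBC strata.

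For units, if the data allow, "unadjusted TRALI rates per number of units transfused will also be calculated". No counting window is given. The primary rate analysis uses Criterion A, which in Table 5 is ICD-9-CM 518.7 in any position.

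Section IV.F.4 says that, if feasible, "a reference category will be defined for variables examined in the primary analysis and unadjusted rate ratios and 95% confidence intervals" will be produced. Component group is one of those variables, and comparing component-specific rates is the first exploratory objective in section II.B.

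On timing, section III.D and Table 1 require onset during or within 6 hours of transfusion (6 to 72 hours for delayed TRALI). Section IV.E looks for the nearest preceding transfusion, but only in chart review. Table 7 holds start and end times for each transfusion.

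**The concern.** An any-exposure stratum carries the risk of whatever else was given in the same stay. The any-plasma rate is partly an RBC and platelet rate. As a labelled description it is a legitimate quantity. As one side of a ratio it is not a component contrast, because the same stays and cases sit on both sides. Nothing in section IV.F.4 stops the ratios from being formed that way, and the any-exposure strata are the ones the protocol treats as standard.

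The second issue is time order. The objective speaks of TRALI following transfusion, but a discharge code has no clock. A case whose plasma was started after the lung injury can be counted as plasma-exposed, and units given during rescue can move a case into a higher unit stratum. Readers would take these tables as component-specific and dose-specific risk.

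**Working it through.** **The plan's own figure.** Section IV.F.5 expects fewer than 200 cases and gives no derivation, so it cannot be reproduced. It is plausible: 2 million inpatient encounters per year (III.B) × 25/12 years × transfused share × 22.5 per 100,000 (the Medicare rate in III.D). An assumed share of 10% gives 416,667 stays and 94 cases; 20% gives 188; 200 cases would need about 21%. The protocol contains no rate-ratio calculation.

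**Overlap: method.** The protocol gives no component mix, so the shares and risks below are assumptions. Stays fall into seven patterns (R = RBC, P = plasma, T = platelets). Risk in a pattern is the sum of its components' risks. The any-P rate is Σ(share × risk) over patterns containing P, divided by Σ share over the same patterns.

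| Mix | R | P | T | RP | RT | PT | RPT |
|---|---|---|---|---|---|---|---|
| Low (10% multi) | 80% | 5% | 5% | 5% | 3% | 0.5% | 1.5% |
| Mid (20% multi) | 70% | 5% | 5% | 10% | 5% | 1% | 4% |
| High (32% multi) | 60% | 4% | 4% | 15% | 8% | 1% | 8% |

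**Worked case: mid mix, risk 15 per 100,000 from each component (true ratio 1.00).**
- Any-P: (0.05×15 + 0.10×30 + 0.01×30 + 0.04×45) / 0.20 = 5.85 / 0.20 = 29.25.
- Any-R: (0.70×15 + 0.10×30 + 0.05×30 + 0.04×45) / 0.89 = 16.8 / 0.89 = 18.88.
- Ratio 29.25 / 18.88 = 1.55. Plasma-only versus RBC-only is 15 / 15 = 1.00.

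**Any-plasma / any-RBC ratio across mixes.**

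| Risks R/P/T per 100,000 | Exclusive ratio | Low | Mid | High |
|---|---|---|---|---|
| 15/15/15 | 1.00 | 1.52 | 1.55 | 1.50 |
| 10/20/20 | 2.0 | 2.31 | 2.11 | 1.87 |
| 10/0/0 | 0 | 0.54 | 0.70 | 0.82 |

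With 400,000 stays and equal risks, 67 to 84 cases are counted 83 to 142 times across the three strata.

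A further assumed mix (R 70%, P 4%, T 4%, RP 9%, RT 6%, PT 1%, RPT 6%) gives:
- Risks 10/0/20: any-plasma is 2.9 / 0.20 = 14.5 per 100,000 although plasma carries no risk.
- Risks 10/50/30: 68.0 / 22.2 = 3.06 against a true 5.0.
- Risks 10/30/20: each case is counted 31.6 / 18.5 = 1.71 times, and 7.2 / 8.9 = 81% of any-plasma cases are also any-RBC cases.

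**Interval.** Mid mix, equal risks, 400,000 stays: any-P has 23.4 cases, any-R has 67.2, and 19.2 are in both. Treating counts as Poisson and the groups as independent, the variance of the log ratio is 1/23.4 + 1/67.2 = 0.0576 (SE 0.24). Allowing for shared cases subtracts 2×19.2/(23.4×67.2) = 0.0244, leaving 0.0332 (SE 0.18). Here the naive interval is too wide, and it is centred on the wrong quantity.

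**Post-onset exposure.** Suppose plasma has no effect and is given in share s of stays, and a fraction q of cases without earlier plasma receive it after onset and are classed as exposed. The plasma versus no-plasma ratio is then approximately [(s + (1−s)q)/s] / (1−q). For s = 10%: q = 5% gives 1.45/0.95 = 1.53, and q = 20% gives 2.8/0.8 = 3.50. For s = 20%: 1.26 and 2.25. Both s and q are assumptions.

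**The case against.** The strongest reply is that this is a descriptive protocol that already contains most of the remedy. The exclusive groups and all four combinations are named in section IV.F.2. The overall rate counts each case once. The ratios are exploratory, conditional on feasibility, and have no reference category yet; year, age, sex and race do not share the overlap problem. Chart review already looks for the nearest earlier transfusion. All of that is right. It limits the weight of the point, but it does not tie the component ratios to exclusive groups.

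Sample size is a fair defence of the conditional wording. Under the last mix with risks 10/30/20, plasma-only holds 1.2/18.5 = 6.5% of cases and platelet-only 0.8/18.5 = 4.3%: about 13 and 9 out of 200, or 6 and 4 out of 100. Making such groups the primary strata would be a precision trade-off, so I do not ask for it. Exclusive groups also remain unadjusted and open to confounding by indication.

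Some stronger readings are tempting, and the documents do not support them:
- *That the plan deliberately counts transfusions given after onset.* It says the reverse in words: TRALI after, or subsequent to, transfusion. What is missing is a rule that enforces this.
- *That units are counted over the whole stay, so the unit gradient is inflated.* No window is stated. Whole-stay counting is the natural reading, but it is an inference, and the size of any inflation has not been calculated.
- *That the plan uses a wrong interval method.* No method is named. The point is only that a standard independent-groups interval would not apply to overlapping groups.

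**Conclusion.** The point holds in this form. The overlap of the strata follows from the any-exposure definition and rests on no assumption. If section IV.F.4 is followed as written, a component ratio can compare groups that share stays and cases. Its size rests on assumed mixes and additive risks: a true 1.00 becomes 1.50 to 1.55, a true 2.0 becomes 1.87 to 2.31, and a true 5.0 becomes 3.06 in one further mix. Because the direction changes with the inputs, a reader cannot correct for it.

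The timing gap is also real, though it is an absence of enforcement and not a stated choice. If it operates at the assumed levels, a null plasma effect could appear as 1.26 to 3.50.

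The overall rate is unaffected by the overlap, and the ratios are exploratory, so this should be corrected but does not undermine the study.

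**What to change.** 1. In section IV.F.2, keep the any-exposure rates, state that the strata overlap and do not sum to the total, and form no between-component ratios from them.
2. In section IV.F.4, compute component rate ratios only between mutually exclusive patterns: RBC-only as reference, against plasma-only, PLT-only and the combinations already listed.
3. For chart-confirmed cases, also tabulate the components and units given before chart-recorded onset, within the protocol's own windows (6 hours; 6 to 72 hours for delayed TRALI). Have the abstraction form, which is still to be developed, record onset date and time.
4. Label the electronic unit-stratified rates as whole-stay and not necessarily pre-onset, if that is how they are counted.

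Cost: items 1, 2 and 4 need wording and programming only. Item 3 uses exposure timing already collected under sections IV.E and IV.F.3. It cannot be programmed for the electronic rates, because Criterion A has no onset time, so it covers only reviewed charts (at most 200). Precision suffers in item 2. In the mid mix with equal risks and 400,000 stays, plasma-only has 400,000 × 0.05 × 15/100,000 = 3 cases and RBC-only 42. The SE of the log ratio is √(1/3 + 1/42) = 0.60, so a ratio of 1.00 would carry an approximate 95% interval of 0.31 to 3.2. Exact methods would be preferable at such counts.

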## 3. Quantification of Algorithm Positive Predictive Value

### a. Outcome

We will examine the positive predictive value of electronic TRALI criteria and diagnosis codes through chart review. Medical chart review will be conducted to validate transfusion exposure details for all TRALI cases determined to be definitive, possible, or delayed TRALI cases without regard to whether a prior transfusion record existed in the electronic claims data.

Charts will be adjudicated according to the workgroup approved TRALI clinical case definitions. We will quantify the positive predictive value for each electronic TRALI criterion, as compared to chart review. We will consider stratifying results by age and gender, and also including analysis for possible TRALI and delayed TRALI. Information about indications for blood transfusion, history of prior events will also be collected for analysis in exploratory objectives.

### b. Exposure

We will examine the positive predictive value of reported transfused blood component exposure (s) of interest as compared to confirmed blood component exposure (s) of interest in identified TRALI cases included in HCA's Sentinel database. Medical chart review will be conducted to validate transfusion exposure details for all TRALI cases determined to be definitive, possible, or delayed TRALI cases without regard to whether a prior transfusion record existed in the electronic data. Medical charts will be reviewed to confirm the blood component exposure, dates and times of exposure, and obtain information about the details of exposure (e.g., if available, the number of units, infusion rate, specific product, processing method, route of administration, transfusion environment). We will quantify the positive predictive value for electronically identified blood component, as compared to blood component exposure confirmed with chart review.

Blood exposures will be identified electronically in HCA's Sentinel database, using the ISBT and Codabar systems and the National Healthcare Safety Network (NHSN)'s blood component mapping system will be used to identify broad blood component categories. Although this primary objective is focused broadly on blood components, if feasible and available, we collect any additional information about blood

component(s) administered (e.g., method of processing) included in charts for analysis in exploratory objectives.

We will use all available data to identify transfusion timing, and will explore the possibility of supplementing chart information with electronically derived timing information (i.e., administration timing as defined in the HCA Sentinel database). In other words, neither the electronic (claims) data nor the medical record data will be pre-specified to be consistently prioritized over the other, rather both will be evaluated and used in establishing the transfusion timing.

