**Table 1: Transfusion Related Acute Lung Injury (TRALI) definitions**

Definition	Clinical Description
Definitive TRALI 	
 
1. No evidence of acute lung injury (ALI) prior to transfusion AND
 
2. ALI onset during or within 6 hours of transfusion AND
 
3. Hypoxemia defined by any of these methods: 
 
•PaO2 / FiO2 ≤300 mm Hg
 
•Oxygen saturation is < 90% on room air
 
•Other clinical evidence
 
 AND
 
4. Radiographic evidence of bilateral infiltrates AND
 
5. No evidence of left atrial hypertension (i.e. circulatory overload) AND
 
6. No temporal relationship to an alternative risk factor for ALI during or within 6 hours of completion of transfusion
 

Possible TRALI 	Same as above EXCEPT there is a temporal relationship to a specific ALI risk factor (Table 2)
Delayed TRALI definition, defined in critically ill patients	
Delayed TRALI 	Same as for possible TRALI except allows for symptom onset within 6 to 72 hours of blood transfusion

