Hospital care setting at the time of TRALI diagnosis (e.g., inpatient, institutional, outpatient, or emergency department), admission type (e.g., emergency, urgent, elective), hospital unit (e.g., coronary care unit, intensive care unit, trauma unit) will also be confirmed and recorded. Transfusion information in identified patients with TRALI will be reviewed to correctly identify the transfusion exposure. For patients with a prior transfusion identified in the HCA Sentinel database, the transfusion record prior to and closest to the TRALI event will be sought, to confirm or correct transfusion date and timing, number of transfused units for each blood component (e.g., RBCs, platelets, plasma, whole blood, autologous transfusion), volume of transfusion, type of blood component transfused, blood component processing (e.g., leukocyte reduced, irradiated) in the HCA Sentinel database. Hospital care setting for the time of transfusion exposure will also be confirmed. The indication for transfusion will be recorded for each patient if present. Use of mechanical ventilation before and after TRALI will also be confirmed. For patients without a prior transfusion recorded in the HCA Sentinel database, if the case is ultimately classified as TRALI, then HCA hospital records will be reviewed to attempt to confirm or correct the absence of a transfusion exposure prior to TRALI onset.

Clinicians will utilize the National Healthcare Safety Network (NHSN) Manual: Biovigilance Component definition of TRALI (summarized in **Table 1** and **Table 2** of this protocol) to diagnose TRALI. Delayed TRALI will be diagnosed in the same manner, but will allow for symptom onset between 6 and 72 hours of the transfusion. The primary analysis will be based on definitive TRALI, secondary analyses will include possible TRALI and delayed TRALI.

Positive predictive value will be determined for each electronic TRALI criterion as compared to definitive TRALI confirmed by clinical adjudicators. PPVs will also be calculated for each electronic TRALI criteria as compared to possible and delayed TRALI as confirmed by clinical adjudicators. The PPV will also be determined for the transfusion exposure as identified in HCA Sentinel data, as compared to confirmed transfusion exposure obtained by clinical adjudicators during chart review.

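### The protocol gives two denominators for the transfusion-exposure PPV, and the narrower one, adjudicated TRALI only, fixes the any-transfusion PPV at 100% and drops records in rejected charts

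*Protocol*

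**What the plan says.** Primary Objective 4 (Section II.A) is to determine by chart review "the positive predictive value of reported transfused product exposure in identified TRALI cases".

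Section IV.F.3.b opens by referring to TRALI cases identified in the electronic database, then narrows the set: "Medical chart review will be conducted to validate transfusion exposure details for all TRALI cases determined to be definitive, possible, or delayed TRALI cases". That sentence goes on to include cases for which the database holds no earlier transfusion. Section IV.F.3.a carries almost the same sentence. The measure named in IV.F.3.b is the PPV of the electronically identified blood component against the chart.

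Section IV.E is wider. Charts are reviewed whatever their transfusion status, up to a cap of 200. The clinicians receive the whole-stay chart and verify both exposure and diagnosis in each case. The closing sentence of IV.E on the exposure PPV has no adjudication condition.

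Section IV.E then splits by electronic record. Where a prior transfusion is recorded, "the transfusion record prior to and closest to the TRALI event will be sought", with no adjudication condition. Where none is recorded, the hospital's records are searched for a transfusion before onset, but the search is conditional: "For patients without a prior transfusion recorded in the HCA Sentinel database, if the case is ultimately classified as TRALI".

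Table 1 makes transfusion part of the outcome. Definitive and possible TRALI need "ALI onset during or within 6 hours of transfusion", and delayed TRALI needs onset 6 to 72 hours after transfusion.

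**The concern.** A PPV for an exposure record should be taken over charts chosen without regard to whether the exposure proves real. Under the wording of IV.F.3, a chart enters only after clinicians have accepted a diagnosis that presupposes a transfusion. A stay whose electronic record has no transfusion behind it can never be accepted, so that type of error is removed before it is counted. The check for unrecorded transfusions has the same dependence.

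This matters because the assessment is the first Sentinel use of this inpatient source (Section I), the transfusion table is new (Section III.B), and Section IV.C warns that codes may be missing or of unknown validity. The same electronic exposure defines the transfused-stay denominator of the incidence rates (Section IV.F.2). A PPV that cannot fall below 100%, or one read as if it covered all records, would give false reassurance.

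**Working it through.** The protocol states no expected PPV, precision or sample-size derivation for exposure validation, and 200 is a cap. There is no planned figure to reproduce. All values of p, s, f, q and v below are assumptions.

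**1. Which charts count**

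| Place | Charts in the exposure check |
|---|---|
| IV.E, review procedure | each reviewed chart |
| IV.E, electronic record present | no adjudication condition |
| IV.E, no electronic record | only if classified as TRALI |
| IV.E, exposure PPV sentence | no adjudication condition |
| IV.F.3.a and IV.F.3.b | only definitive, possible or delayed TRALI |

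These cannot all define one denominator.

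**2. Any-transfusion PPV under IV.F.3**

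Within adjudicated TRALI, let p be the true exposure prevalence, s the sensitivity of the electronic record and f its false-positive rate. Then PPV = p·s / (p·s + (1−p)·f). Table 1 makes p = 1, so PPV = s / (s + 0·f) = 100%. This was checked for s of 0.70, 0.90 and 0.99 with f of 0.01, 0.10 and 0.30, and the result was 100% each time. It applies at stay level, with any charted transfusion counting as confirmation.

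**3. Component PPV under IV.F.3**

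Here p is the share of adjudicated cases that truly received the component, so p < 1. With s = 0.95:

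| p | f = 0.01 | f = 0.05 | f = 0.10 |
|---|---|---|---|
| 0.2 | 96.0% | 82.6% | 70.4% |
| 0.4 | 98.4% | 92.7% | 86.4% |
| 0.8 | 99.7% | 98.7% | 97.4% |

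For example, 0.2×0.95 / (0.2×0.95 + 0.8×0.10) = 0.19/0.27 = 70.4%. This PPV can fall well below 100%. It still omits every record in a rejected chart, and a record with no transfusion behind it is wrong for whatever component it names.

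**4. Any-transfusion PPV over all reviewed charts with an electronic record**

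Let q be the share of these charts adjudicated as TRALI and v the PPV in the rest. Then PPV = q·1 + (1−q)·v.

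| q | v = 0.80 | v = 0.90 | v = 0.98 |
|---|---|---|---|
| 0.2 | 84.0% | 92.0% | 98.4% |
| 0.4 | 88.0% | 94.0% | 98.8% |
| 0.6 | 92.0% | 96.0% | 99.2% |

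**5. One illustration in counts (any transfusion only)**

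Assume 200 charts reviewed, 190 with an electronic transfusion, 10 of those false, and 40% of the 200 (80) adjudicated TRALI, all 80 with an electronic record.

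- All charts with a record: 180/190 = 94.7% (Wilson 95% CI 90.6 to 97.1).
- Adjudicated TRALI only: 80/80 = 100% (exact 95% CI 95.5 to 100).

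The second interval excludes 94.7%. At a PPV near 95%, the half-width 1.96·√(0.95×0.05/n) is 4.8 points at n = 80 and 3.1 points at n = 190.

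**6. The search for unrecorded transfusions**

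It starts after a TRALI classification, which under Table 1 already needs a transfusion. Of its two intended outcomes, confirming or correcting the absence, the first cannot occur. Charts with no record that are not classified as TRALI are outside it.

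**The case against.** The strongest reply is that IV.E already does what is wanted: charts are reviewed whatever their transfusion status, exposure is verified in each case, and the PPV sentence is unrestricted. This stands as a reading. It does not settle the matter, because the two subsections that describe the PPV analysis state the narrower set.

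A reader might infer that unrecorded transfusions are not sought. The documents do not support that. IV.F.3.b includes cases with no prior record, and IV.E plans a records search for them. Applying Table 1 also makes clinicians look for a transfusion, so a miss can surface during adjudication. What remains is that the stated search is conditional on classification and no count of misses is named.

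A reader might also infer that Objective 4 cannot be answered. It concerns the transfused product, and IV.F.3.b measures it per component. A case can have red cells recorded and plasma in the chart, so error can show even among adjudicated cases (step 3).

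Nor is it true that a chart with a false record can never be adjudicated TRALI, since a different, real transfusion may lie in the window. Finally, Objective 4 is confined to identified TRALI cases and Section IV.F.5 expects descriptive analyses. Both points lower the stakes, but neither resolves the conflict.

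**Conclusion.** The protocol contradicts itself on the denominator of a primary estimate. On the IV.F.3 wording, a stay-level any-transfusion PPV is 100% by construction and carries no information. Over all reviewed charts with a record it would be 84.0% to 99.2% under the assumed q and v. The counts of 190, 10 and 40% are likewise assumptions and bear on the any-transfusion PPV only.

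The component PPV stays informative but is selective. Leaving out rejected charts probably raises it. The documents give no basis for the size, and the direction is an inference, not a calculation. It should not be carried over to transfused stays in general.

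The search for unrecorded transfusions exists, but it cannot confirm an absence and does not extend beyond classified cases. This should be fixed, ideally before the abstraction form is final. It does not defeat the objective.

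**What to change.** 1. Reconcile Section IV.E with IV.F.3.a and IV.F.3.b, and state one denominator.
2. Compute the exposure PPV, overall and per component, over all reviewed charts with an electronic transfusion record, whatever the adjudication. Show adjudicated TRALI as a subgroup.
3. In all reviewed charts without a record, look for a transfusion before TRALI is classified, and report how many are found.
4. Abstract every transfusion in the 6 hours before onset (72 hours for delayed TRALI), not only the closest one. The incidence rates in IV.F.2 count any component given during the stay, so confirming a single record does not check that classification.

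The cost is modest: extra abstraction fields and clinician time in whole-stay charts that are already being pulled. No further charts are needed.
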